The evolution of the pulse oximetry sensors to incorporate multi-wavelength technologies provided the opportunity to modify the PVi algorithm and improve clinical performance. As a dynamic monitor of cardiac function, PVi/ RPVi is analogous to pulse pressure variation (PPV), which may be derived through minimally-invasive means using beat-to-beat arterial pressure expressed as a percentage by the Philips IntelliVue (Philips Labs, Noord Brabant, NL) or stroke volume variation (SVV), which may be derived through minimally-invasive means using pulse contour analysis of the arterial pressure waveform as done by the Vigileo/Flotrac System (Edwards Labs, Irvine, CA) or Philips IntelliVue (Philips Labs, Noord Brabant, NL). Multiple studies have demonstrated that PPV and/or SVV is a valuable tool in predicting fluid responsiveness in mechanically ventilated patients.

The aim of this study is to test the ability of RPVi to predict fluid responsiveness in mechanically ventilated patients in the operating room and to compare it to other dynamic monitors of cardiac function in this setting.

This study will include patients [REDACTED] undergoing cardiac surgical procedures in which pulmonary and peripheral arterial catheters are standard monitors used for continuous monitoring of cardiac function and blood pressure, respectively. Patients with cardiac arrhythmias and intracardiac shunts will be excluded. Patients will be assigned to one of the two study groups with different tidal volumes: 6 ml/kg IBW and 8 ml/kg IBW. Both tidal volumes are within the range that is commonly used intra-operatively. In patients without significant pulmonary disease there is no significant risk or benefit associated with either tidal volume, however, there is evidence of decreased utility of the dynamic monitors of cardiac function (PPV/SVV) at lower tidal volumes. Attention to the tidal volume will aid the assessment of the utility of RPVi as a monitor of cardiac response to fluid administration.

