8 STATISTICAL PLAN

Prior studies of the predictive abilities of dynamic monitors of cardiac function with respect to cardiac output have established that sample sizes of 50 patients are sufficient to characterize the performance of the monitor. However, based on an ongoing Masimo study at another clinical test site, preliminary data received suggests that, of the first 83 subjects enrolled approximately 29% were responders. Therefore, in order to analyze the ability of RPVi, the sample size will be increased to a total of up to 150 patients. The first group of up to 100 subjects will be used to gather data to determine the thresholds for fluid responsiveness that would be used for the second group of 50 subjects. The second group will be the validation set to be used to evaluate study objectives in **section 2.1**. As such, the study will be registered on ClinicalTrials.gov but only results from the validation phase will be posted.

Normality of distribution will be tested before any statistical evaluation by using the Kolmogorov- Smirnov method. Descriptive statistical data will be reported as mean \pm SD. Except for the bias between both methods (RPVi vs PPV/SVV and SV/CO measurements). Comparisons between PPV/SVV and RPVi and between CO/SV measurements will be performed with a paired student t test. PPV/SVV and RPVi as well as SV/CO measurements will be compared using Bland and Altman. In order to evaluate the ability of RPVi to reliably detect changes in PPV/SVV and for CO measurements to accurately track Flotrac CO changes we will use a method based on polar plotting of PPV/SVV and RPVi and CO measurements changes over consecutive cycles as described by Critchley et al. We will exclude from this analysis small changes of mean value of

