PPV/SVV and RPVi and CO measurements less than 3%. In this method, a good trending ability requires an angular bias no greater than ± 5 degrees and a SD for the polar angle of less than ± 15 degrees. In this method, simultaneous changes of each indices of consecutive validated respiratory cycle will be reported on a polar plot. The polar angle will be derived from the ratio of the changes of the two indices such a ratio close to one led to a null angle with the x axis, this angle approach a 90 degrees angle when the ratio diverges from one. The radius will be the mean of the simultaneous changes of the two indices between two consecutive validated respiratory cycles. In these conditions a mean angle and its SD can be calculated.

The strength of linear dependence between PPV/SVV and RPVi and SV/CO measurements for all patients will be measured by the Pearson coefficient of correlation. The mean of correlation coefficients and comparison between correlation coefficients will be performed after a Fischer's transformation. In order to analyze the ability of RPVi to correctly classify the respiratory cycle as responder or non-responder after a volume loading in respect to a theoretical threshold value of PPV/SVV of 12%, we will measure the area under the curve of a Receiver Operating Characteristic (ROC) curve. Then the selected value of RPVi for each patient will be the one which maximized the Youden index (sensitivity + (specificity - 1)). The agreement between the two classifications will be quantified by the Kappa score for each patient, taking as threshold value of RPVi the individual value determined by the ROC curve. The reported mean values of areas under ROC curves and Kappa scores will be therefore calculated from the individual values. Taking the intra patients coefficient of correlation as a dependent variable, we will estimate its relationship with potentially explanatory variables by using univariate analysis, including Student t test for qualitative data and correlation for quantitative data and multivariate analysis by multiple linear regression. Categorical binary variable will be transformed into dummy variables. Other correlations will be evaluated by Pearson coefficient.

For all comparisons, a P value < 0.05 will be considered significant. Statistical analysis will be performed using SPSS software version 13.0 for Windows (SPSS Inc., Chicago, IL).

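### Does the unstated unit of the 3% exclusion in the polar-plot analysis leave the trending verdict open?

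*Combined protocol and SAP*

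**What the plan says.** Section 8 compares changes in RPVi with changes in PPV/SVV, and changes between cardiac output (CO) measurements, on polar plots over consecutive respiratory cycles, following a cited published method. The exclusion rule is one sentence. It begins "We will exclude from this analysis small changes of mean value of" and ends "PPV/SVV and RPVi and CO measurements less than 3" per cent. The performance limits come next: "a good trending ability requires an angular bias no greater than" 5 degrees either way, and an SD of the polar angle below 15 degrees.

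On construction, section 8 says "The polar angle will be derived from the ratio of the changes of the two indices", with a ratio near one giving a null angle, and "The radius will be the mean of the simultaneous changes of the two indices between two consecutive validated respiratory cycles". It does not say whether the changes are relative or in index points, or whether the mean is signed or absolute.

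Section 1.1 shows that the indices are already percentages. RPVi is defined with a factor of 100%, and PPV is obtained "using beat-to-beat arterial pressure expressed as a percentage by the Philips IntelliVue". Section 8 also uses a "theoretical threshold value of PPV/SVV of 12" per cent to classify cycles in the ROC analysis.

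**The concern.** For an index that is itself a percentage, 3% has two possible meanings, and at a level of 12% they differ more than eightfold. A polar angle is unstable when both changes are small, because noise then dominates their ratio. The size of the cut therefore largely determines the angular SD.

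Among the planned comparisons of RPVi with PPV/SVV, the polar analysis is the only one with numerical performance limits. If the unit were chosen after the data were seen, the same data could be reported as good or poor trending. The unit in which changes are plotted raises a related question for the bias limit when the two indices sit at different levels. Section 8 treats that difference as open: "Comparisons between PPV/SVV and RPVi and between CO/SV measurements will be performed with a paired student t test".

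**Working it through.** The plan derives nothing from the 3% cut, so it has no figure of its own to reproduce.

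**1. Unit conversion (plan figures only).** Relative: 0.03 × 12 = 0.36 points. Points: 3. Ratio: 3 / 0.36 = 8.3.

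**2. Effect of the cut on the angular SD (assumed inputs).** The documents give no SD, correlation or level for cycle-to-cycle changes. Assumptions: paired changes x and y are bivariate normal with mean zero and equal spread, the correlation is 0.9 and the level is 12%. The angle is atan((x − y)/(x + y)). A pair is kept if (|x| + |y|)/2 reaches the cut. Each setting used at least 2 million simulated pairs.

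| Change SD (points) | SD of angle, cut 0.36 (kept) | SD of angle, cut 3 (kept) |
|---|---|---|
| 1 | 21.0° (74%) | 4.0° (0.2%) |
| 1.5 | 25.5° (86%) | 5.5° (4%) |
| 2 | 27.4° (92%) | 6.9° (12%) |
| 3 | 28.8° (96%) | 9.1° (31%) |
| 5 | 29.5° (99%) | 13.4° (54%) |
| 10 | 29.9° (over 99%) | 23.4° (80%) |

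At this correlation the 15-degree verdict changes for SDs of 1 to 5, and both readings fail at 10. At a change SD of 3, passing needs a correlation of about 0.98 with the relative cut and 0.77 with the points cut. Above about 0.99 both pass.

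A second model, true change plus measurement error, behaves alike. With a true-change SD of 3, an error SD of 0.75 (correlation 9/9.5625 = 0.94) and a cut on the signed mean, the angular SD is 19.0 degrees with 91% kept, against 7.2 degrees with about a third kept. With an error SD of 0.25 the verdict did not change in any setting tried.

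**3. Effect of the cut on the angular bias.** With equal spreads the mean angle stays at zero under either cut. With one index moving 1.1 to 1.3 times as much as the other, a correlation of 0.9 and change SDs of 1.5 to 5, going from 0.36 to 3 points shifted the mean angle by about 0.25 to 1.25 degrees. In that grid the 5-degree verdict changed only at a ratio of 1.2, where the bias without noise is atan(0.2/2.2) = 5.2 degrees, already at the limit.

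**4. Plotting unit, a separate matter from the cut.** If both indices move in proportion and their levels have ratio k, the angle is 0 in relative units and atan((k − 1)/(k + 1)) in points, which exceeds 5 degrees above k = tan 50° = 1.19. If instead both move by equal points from 12 and 15, the angle is 0 in points and atan(12/15) − 45° = −6.3 degrees in relative units. The documents support neither pattern over the other, so this does not count against either unit.

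**5. What the sentence allows.** Its list is PPV/SVV, RPVi and CO, with one 3%. For CO, a flow, only a relative change makes sense. The points reading needs the same figure to carry two meanings within one sentence.

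**The case for a change.** The strongest case for acting is that the text never says relative, and that the cited method, judged by its title in the reference list, was written for cardiac output monitors, where the question does not arise. The plan extends it to percentage-valued indices without comment. Across a plausible range the unit alone separates failing from passing, and one sentence written before the validation set is analysed would prevent a choice made after seeing results. That the unit is unstated, and that the 15-degree verdict can depend on it, both stand.

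The signed-or-absolute question has some force too. With the relative cut, a change SD of 1.5 and a correlation of 0.95, a signed mean gives 14.0 degrees and passes, while an absolute mean needs a correlation of about 0.96. A signed mean also drops discordant pairs preferentially. But section 8 adopts the cited method by name, and a convention not repeated in the plan is not thereby missing from the method. That source is not available here, so its silence cannot be shown.

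The rest is weaker. The 5-degree verdict is hardly affected by the cut, and the claim that a points cut removes most pairs fails at larger spreads (54% kept at SD 5, 80% at SD 10).

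**Conclusion.** This is missing detail that an analyst would fill sensibly, and the plan need not change. The shared cut with CO points to a relative change for every quantity in the list. At 12% that is 0.36 points, and it keeps 74% or more of pairs in the settings tabulated, so the analysis is usable as written. The relative reading also gives the larger angular SD in every tabulated row, so taking the sentence at face value does not favour the device.

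The stakes are limited. The first hypothesis in section 2.1 concerns prediction of a rise in cardiac output. The second concerns changes after the fluid bolus and names no polar limit. Correlation, Bland-Altman, ROC and kappa results are reported alongside. Writing the unit down would record the natural reading without altering the analysis.

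The sizes rest on assumed change SDs of 1 to 10 points, a correlation near 0.9, a level of 12% and normal changes, none of which the documents supply. The 0.36 against 3 points is plain arithmetic. The conclusion would weaken if the analysis were run with a points cut for the indices and a relative one for CO, which the sentence as written does not support.

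### Section 8 has repeated cycle-level pairs per patient, but its RPVi v PPV/SVV paired t test and Bland-Altman state no unit or patient term, and the polar plot does not handle within-patient correlation

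*Combined protocol and SAP*

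**What the plan says.** Section 8 gives the two agreement methods one sentence each: "Comparisons between PPV/SVV and RPVi and between CO/SV measurements will be performed with a paired student t test", and "PPV/SVV and RPVi as well as SV/CO measurements will be compared using Bland and Altman". Neither sentence says whether a pair is a cycle, a time point or a patient, and neither names a repeated-measures form.

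The polar plot does name its unit, the change from one cycle to the next: "simultaneous changes of each indices of consecutive validated respiratory cycle will be reported on a polar plot", and "The radius will be the mean of the simultaneous changes of the two indices between two consecutive validated respiratory cycles". The summary is a single step: "In these conditions a mean angle and its SD can be calculated". Good trending requires an angular bias within 5 degrees and "a SD for the polar angle of less than ± 15 degrees". Changes under 3% are left out.

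For ROC and kappa the same section works by patient: "The reported mean values of areas under ROC curves and Kappa scores will be therefore calculated from the individual values". It also uses a within-patient correlation coefficient as an outcome in a regression. All comparisons are judged at P < 0.05. Section 7 plans one baseline and one repeat set of SV/CO measurements, before and after the volume expansion. Section 4.1 gives the validation set 50 subjects.

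**The concern.** A kappa, an ROC threshold and a correlation for each patient cannot be computed from one pair per patient, so the RPVi v PPV/SVV data must hold repeated pairs. A plain paired t test assumes independent pairs. Pairs from one patient share that patient's typical gap between the two indices, so they are not independent evidence about the mean gap.

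The t test carries weight. The second null hypothesis in section 2.1 is that changes in RPVi do not differ from concurrent changes in PPV/SVV, and this is the only named test of a mean difference between them. With the unit left open, cycle or patient can be chosen after the data are seen, and that choice decides whether the P value is valid.

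**Working it through.** The plan gives no standard error, interval, number of cycles or within-patient correlation for these analyses, so there is no figure of its own to reproduce. The check asks what happens to the t test if repeated pairs are treated as independent.

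**Inputs.** From the documents: 50 patients (section 4.1) and alpha 0.05 (section 8; two-sided assumed, as sidedness is not stated). Assumed: *m* pairs per patient, and an intraclass correlation (ICC) of the paired difference within patient.

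**Formulas.** Design effect DE = 1 + (m − 1) × ICC. A pooled interval for the mean difference is too narrow by a factor √DE. The true rejection rate of the nominal 5% test is 2 × [1 − Φ(1.96/√DE)].

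**Example.** With m = 10 and ICC = 0.3, DE = 1 + 9 × 0.3 = 3.7. Then √DE = 1.92, 1.96/1.92 = 1.02, and the rejection rate is 31%.

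| Pairs per patient | DE (ICC 0.3 / 0.5) | √DE | True rejection rate |
|---|---|---|---|
| 1 | 1 / 1 | 1 / 1 | 5% / 5% |
| 2 | 1.3 / 1.5 | 1.14 / 1.22 | 9% / 11% |
| 5 | 2.2 / 3.0 | 1.48 / 1.73 | 19% / 26% |
| 10 | 3.7 / 5.5 | 1.92 / 2.35 | 31% / 40% |
| 30 | 9.7 / 15.5 | 3.11 / 3.94 | 53% / 62% |

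At an ICC of only 0.1 with 10 pairs, DE = 1.9 and the rate is about 16%. The number of patients does not enter the formula, so enrolling more would not cure the problem.

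**Simulation check** (50 patients, 2,000 runs per setting). At ICC 0.3 and 0.5 the pooled test rejected in 31% and 40% at 10 pairs, and in 52% and 63% at 30. A t test on patient means rejected in 4.4% to 6.4% over all settings tried (10, 30 or 100 pairs; ICC 0.1 to 0.7).

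**What pooling does not change.** In the same simulation the SD of the pooled differences was 0.99 to 1.00 of the true total SD. The limits of agreement are built from that SD, so their width hardly moves. By the same argument the SD of the polar angle hardly moves against 15 degrees.

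**Polar plot.** A constant patient offset cancels in a change from one cycle to the next. In a simulation of mean changes with constant offsets and independent cycle noise (31 cycles, ICC 0.3), the naive standard error was 0.031 against an actual 0.005: too large, not too small. The angle, however, depends on the ratio of the two changes, so a patient-specific gain (RPVi moving more or less than PPV/SVV) does not cancel. A naive interval for the mean angle is therefore unreliable, with a size and direction that the documents do not settle.

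**The case against.** A reader might infer that all three analyses are laid down on pooled cycles as if each were a separate subject, and that the resulting error bars are far too narrow. The documents do not support that. Only the polar plot is explicitly at cycle level; the t test and Bland-Altman leave the unit unstated. No standard error or interval is specified for the polar plot or Bland-Altman, and the trending limit is an SD, which does not shrink as cycles are added. Where section 8 does state how patients enter (ROC, kappa, within-patient correlation), it works by patient. An analyst might well do the same for the t test, and then nothing is inflated.

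The SV/CO comparisons are also little exposed. With one baseline and one repeat set, at most two pairs per patient arise, and the rate is about 9-11% at the same ICCs. Timing details in section 7 are redacted, so the missing number of cycles is not counted against the plan.

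All of this stands, and it limits the point to an unstated unit with a conditional consequence. It does not remove the point. Section 8 spells out per-patient handling for ROC and kappa and says nothing comparable for the t test, Bland-Altman or polar plot. As named, those methods are the one-pair-per-subject forms, set beside data with repeated pairs.

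**Conclusion.** The point holds as a gap in specification. If repeated RPVi v PPV/SVV pairs enter the paired t test as independent, its P value is too small: the true rejection rate is about 19-26% at 5 cycles per patient, 31-40% at 10 and 53-62% at 30, against a nominal 5%. These figures rest on an assumed ICC of 0.3 to 0.5, assumed cycle counts and equal correlation among a patient's pairs. With one value per patient there is no inflation.

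Any interval put around the bias or the limits of agreement from pooled cycles would be too narrow for the same reason, and one around the mean angle would be unreliable. The finding does not extend to the 15 degree criterion or the width of the limits, which are nearly unchanged. Nor does it show that the trending verdict itself would be wrong. The change should be made: it is cheap and fixes the unit before the data are seen.

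**What to change.** In section 8:

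1. Run the RPVi v PPV/SVV paired t test on one value per patient: the patient mean, or the post-minus-pre bolus change for the second hypothesis in section 2.1.
2. Use the repeated-measures form of Bland-Altman, with between- and within-patient variance components from a random patient effect. Take intervals for the bias and limits by resampling patients.
3. For the polar plot, hold the total angular SD (between plus within patient) against the 15 degree limit, and give intervals for the mean angle and the SD by resampling patients. Do not average per-patient SDs, because that drops the between-patient spread and loosens the criterion. For example, a within-patient SD of 10 and a between-patient SD of 12 (both assumed) give a total of √(100 + 144) = 15.6, which fails, while the averaged within-patient SD of 10 passes.

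The cost is a change of wording and slightly more analysis work, with less favourable P values and intervals. No extra patients or measurements are needed.

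### The polar-plot radius and 3% exclusion in section 8 do not specify absolute changes; on the plain reading opposite-direction pairs cancel, are preferentially dropped, and the polar SD is understated

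*Combined protocol and SAP*

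**What the plan says.** Section 8 assesses whether RPVi tracks PPV/SVV, and whether CO measurements track the comparator's CO, by polar plot: "we will use a method based on polar plotting of PPV/SVV and RPVi and CO measurements changes over consecutive cycles". It cites a published method for this and then restates the rules itself.

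- Exclusion: "We will exclude from this analysis small changes of mean value of" "PPV/SVV and RPVi and CO measurements less than 3" per cent (one sentence, split by a page break).
- Radius: "The radius will be the mean of the simultaneous changes of the two indices between two consecutive validated respiratory cycles".
- Angle: "The polar angle will be derived from the ratio of the changes of the two indices". A ratio near one gives zero degrees, and "this angle approach a 90 degrees angle when the ratio diverges from one".
- Pass mark: "an angular bias no greater than ± 5 degrees" and "a SD for the polar angle of less than ± 15 degrees".

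The section says neither signed nor absolute for the radius or the exclusion. It does not tie the 3% rule to the radius explicitly. It also does not say whether 3% is a relative change or three percentage points, although section 1.1 describes RPVi and PPV as percentages themselves.

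**The concern.** An exclusion zone should remove pairs in which little happened, because their angle is mostly noise. A change in the mean of two indices is half the sum of the two changes, so it is small in two different situations: both indices barely moved, or both moved substantially in opposite directions. The second situation is the clearest evidence of poor trending. If those pairs are removed as small changes, the SD of the angle is computed on a sample from which the worst disagreements have been taken out.

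This matters because the polar plot carries an explicit pass mark, and because the second hypothesis in section 2.1 concerns concurrent changes in RPVi and PPV/SVV. The angle description adds to the difficulty. It suggests that any diverging ratio tends to 90 degrees, which obscures that only opposite-direction pairs lie beyond 45 degrees.

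**Working it through.** The plan states no sample size, power or error rate for the polar analysis, so there is no figure of its own to reproduce.

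**Inputs from section 8:** cut of 3%; zero angle at ratio one; limits of 5 degrees (bias) and 15 degrees (SD). **Assumed, because the documents give neither:** SD of the changes 3, 5, 10 or 20 in the same unit as the cut; correlation r from 0 to 0.95; equal SDs, no bias, bivariate normal changes.

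**Step 1, the angle.** For changes x and y, the angle from the line of equality is arctan(y/x) - 45 degrees, folded to lie within ±90.

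- y/x = 1: 45 - 45 = 0
- y/x = 2: 63.4 - 45 = 18.4
- y/x infinite: 90 - 45 = 45
- y/x = 0: 0 - 45 = -45
- y/x = -1: -45 - 45 = -90

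A ratio diverging to 0 or infinity therefore stops at 45 degrees in size. Only a ratio of -1 reaches 90.

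**Step 2, why the exclusion is selective.** Let R = √(x² + y²) and let θ be the angle above. The size of the net mean |x + y|/2 equals R·cos θ/√2. At θ = 90 degrees it is zero whatever R is. For +10/-5: R = 11.18 and cos 71.6° = 0.316, so 11.18 × 0.316/1.414 = 2.5.

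**Step 3, worked pairs.**

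| Pair | Net mean | Mean of absolute changes | Size of angle | Net-mean rule | Absolute rule |
|---|---|---|---|---|---|
| +10/-10 | 0 | 10 | 90 | dropped | kept |
| +10/-5 | 2.5 | 7.5 | 72 | dropped | kept |
| +10/-2 | 4 | 6 | 56 | kept | kept |
| +20/-10 | 5 | 15 | 72 | kept | kept |
| +3/+3 | 3 | 3 | 0 | kept | kept |

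**Step 4, simulation.** 2,000,000 pairs per setting. A pair is dropped if |net mean| < 3 (net rule) or if the mean of the absolute changes is < 3 (absolute rule). For same-direction pairs the two quantities are equal, so those losses are identical.

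| SD, r | Opposite-direction pairs dropped, net / absolute | Same-direction pairs dropped, both rules | Polar SD in degrees, net / absolute |
|---|---|---|---|
| 5, 0 | 84.3% / 36.5% | 36.5% | 33.0 / 52.4 |
| 5, 0.7 | 95.0% / 71.8% | 32.7% | 20.0 / 29.5 |
| 5, 0.9 | 99.8% / 97.4% | 37.2% | 12.3 / 13.4 |
| 5, 0.95 | 100.0% / 99.9% | 39.5% | 8.9 / 8.9 |
| 10, 0.7 | 71.3% / 27.2% | 9.9% | 26.0 / 36.0 |
| 10, 0.9 | 90.3% / 60.0% | 13.1% | 17.0 / 23.4 |
| 10, 0.95 | 97.4% / 83.7% | 15.6% | 12.7 / 15.6 |
| 20, 0.95 | 77.4% / 36.4% | 4.7% | 16.6 / 22.4 |

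At SD 10, r=0.7, opposite-direction pairs are 25.3% of all pairs. They make up 9.7% of those analysed under the net rule and 21.5% under the absolute rule. The mean angle stays within about 0.1 degree of zero throughout. Of the 24 settings run (four SDs, six correlations), the 15-degree verdict differs between the rules in one: SD 10, r=0.95.

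**The case against.** The strongest reply is that the text never says signed. A radius is a length, so absolute changes are a natural intention. Read with complete literalness, a signed mean below 3% would also exclude every pair in which both indices fall. The check above had to take the size of the net mean to avoid that, and once an absolute value must be supplied, it could equally be placed on each change. The plan also speaks of angles near 90 degrees, which under a net mean would have radius zero and never be analysed. The 3% sentence could instead be read as applying to each index separately. Finally, the cited method may settle the definition, but it cannot be consulted here.

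This stands as far as intent goes: the documents do not establish that the net mean was meant. It does not remove the point. A change in the mean value of two indices is, in ordinary usage, a net quantity. The radius sentence agrees with that, and reading absolute changes means adding a word. An analyst following section 8 could reasonably program the net mean.

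A reader might infer more than the documents support:

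- That all opposite-direction pairs are lost. They are not; +10/-2 and +20/-10 stay in.
- That an index which often moves the wrong way would pass. In every setting run with r of 0.7 or below, the polar SD exceeds 15 degrees under either rule.
- That a perfectly inverse index would have every pair excluded and so look good. That needs equal magnitudes, and with no pairs left there is no verdict rather than a pass.

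The other section 8 analyses (Pearson correlation, Bland-Altman, ROC, Kappa) carry no stated 3% exclusion and could still show a wrong-way index.

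**Conclusion.** The point holds as an under-specified rule whose plain reading favours the device. If the net mean is used, discordant pairs with a net mean below 3% are preferentially removed and the SD of the polar angle is understated; the mean angle is unaffected in the symmetric cases examined. The understatement can be large (20.0 against 29.5 degrees), but it reverses the verdict only at high correlation and only for some SDs (12.7 against 15.6). It vanishes when changes are small and highly correlated (8.9 under both).

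All of these sizes rest on assumed normal changes with equal SDs. They depend on the ratio of the SD to the cut, and so on the undefined unit of the 3%. The error in the angle description needs no assumption: it follows from the geometry.

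Severity is moderate. It would be tempting to treat this as undermining the study's main conclusion. The documents do not support that, because the polar plot is a supporting trending analysis and does not test whether RPVi predicts fluid responsiveness.

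**What to change.** Amend section 8 before the validation data are analysed:

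1. Use the mean of the absolute changes of the two indices for both the radius and the 3% exclusion.
2. State whether 3% is a relative change or percentage points.
3. Define the angle as the arctangent of the ratio of changes minus 45 degrees, folded to ±90, with opposite-direction pairs kept and plotted beyond 45 degrees. Delete the statement that a diverging ratio tends to 90 degrees.
4. Report the number and share of opposite-direction pairs before and after exclusion.

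The cost is a few sentences in the plan and a few lines of code; no further patients or data are needed. The downside is that the reported polar SD may be less favourable.
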